7.2 Pregnancy History

The mothers' history of prior pregnancies as collected on the Pregnancy History eCRF at the Screening Visit will be presented in tables by arm and by site. Summary statistics appropriate for the measurement scale as described in Section 5 will be presented for the following: number of full term live births (≥ 37 weeks), number of premature live births (less than 37 weeks), number of spontaneous fetal deaths and/or still births (≥ 20 weeks), number of spontaneous abortions (less than 20 weeks), number of therapeutic/elective abortions, number of ectopic pregnancies, and whether the participant has a history of pregnancy complications or fetal/infant congenital anomalies (yes/no). In addition, the total number of prior pregnancy outcomes will be calculated by summing these numbers of reported births and abortions from the categories above.

7.3 Pelvic Exam

The mothers' baseline results from the pelvic exam as collected on the Pelvic Exam eCRF at Screening and Enrollment will be presented in tables by arm and by site. Number and percentage of participant-visits for which any abnormal finding was reported will be presented, as well as the number and percentage of specific types of pelvic exam findings.

7.4 Sexually Transmitted Infections

The mothers' baseline sexually transmitted infections (STIs) testing results as collected on the STI Test Results eCRF at Screening (and if indicated at Enrollment) will be presented in tables by arm and by site. Summaries (as described in section 5) of testing results will be presented for the following: pH, bacterial vaginosis, wet prep for candidiasis (buds and/or hyphae[yeast]), trichomonas (TV), syphilis screening and confirmatory test, urine NAAT for gonorrhea (GC), chlamydia (*C. trachomatis*, CT), and hepatitis B surface antigen.

8. PRIMARY ENDPOINT ANALYSES

Analysis (see Section 3.1) will be performed to summarize the frequency of primary endpoints by study arm. Consistent with the primary objectives to describe the safety profile and drug detection in each arm, the number and the percentages of participant experiencing each primary endpoint will be tabulated by study arm. Each participant will contribute once in each category (i.e. only for highest severity AE for each participant) for calculation of event rates. An exact binomial confidence interval (CI) will be calculated for each primary endpoint.

8.1 Maternal Adverse Events

The number and percentage of mothers with 1) serious adverse events (SAEs) and 2) Grade 3 or higher AEs will be tabulated by study arm. Each participant will contribute once for the calculation of the event rates. The estimated rates with exact binomial 95% confidence intervals (CIs) will be calculated by study arm.

See section 10.1 for a description of additional summaries of AEs.

8.2 Infant Adverse Events

The number and percentage of infants with 1) serious adverse events (SAEs) and 2) Grade 3 or higher AEs will be tabulated by study arm. Each participant will contribute once for the calculation of the event rates. The estimated rates with exact binomial 95% CIs will be calculated by study arm.

8.3 Drug Detection

The proportion of participants with detectable drug levels in each study arm for each sample type will be summarized using descriptive statistics in tables by arm and by site. Participants with a drug level for the assigned study product arm above the lower limit of quantification (LLOQ) for any visit after Enrollment will be considered to have a detectable drug level; otherwise, the participant will be considered to have an undetectable drug level.

Drug concentration levels will be summarized using geometric mean, geometric coefficient of variation (CV), arithmetic mean, standard deviation (SD), median, interquartile range (IQR), and range (minimum, maximum). In addition, the number and percentage of participants with detectable and undetectable drug levels will be reported. The CV will be calculated as $100 \times \text{standard deviation (SD)} / \text{Mean of the concentration values}$. Figures for concentration values will be presented using the log scale.

For drug concentrations that fall below the corresponding assay's LLOQ, we will use a value equivalent to half the LLOQ. The number of days to each sample collection will be calculated using the Enrollment date and the date of sample collection as reported in the drug concentrations dataset from the SCHARP Lab Data Management group. For mothers, the time points for drug concentration sample collections are on Visits 3-8 (Week 1 to 2 weeks after product use end visit [PUEV]). Dried blood spot (DBS) samples are collected from mothers at Visit 2, Enrollment in addition to Visits 3-8. For infants, the time points for drug concentration sample collections are on Visits 4-8 (Week 2 to 2 weeks after PUEV).

For the mothers on the DPV VR arm, concentrations of DPV from plasma and breast milk will be reported for each visit in a table by study site. For infants of mothers on the DPV VR arm, concentrations of DPV from plasma will be reported for each visit in a table by study site. Box plots with median DPV levels of plasma concentrations for mothers and infants and of breast milk concentrations for mothers will be presented over the study visit timepoints.

For mothers on the Truvada arm, concentrations of FTC-TP and TFV-DP from DBS and FTC and TFV from breast milk will be reported for each visit in a table by study site. For infants of mothers on the Truvada arm, concentrations of FTC-TP and TFV-DP from DBS will be reported for each visit in a table by study site. Box plots with median drug concentration levels of DBS concentrations for mothers and infants and of breast milk concentrations for mothers will be presented over the study visit timepoints.

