7.4.4 Visit 8 – Study Exit Visit (SEV) - Two weeks after PUEV

The Visit 8, Study Exit Visit (SEV) will occur two weeks (i.e., approximately 14 days) after the PUEV. This visit can occur no earlier than 7 days before the target data and no later than 14 days after the PUEV.

Table 13: Visit 8 – SEV (2 weeks after PUEV) - Mothers

Visit 8 – SEV (2 weeks after PUEV) - Mothers									
Component	Procedures								
Administrative and Regulatory	
 • Review/update locator information • Provide reimbursement • Schedule next visit/contact* 								
Behavioral/Counseling	
 • Social harms assessment • HIV pre- and post-test counseling • HIV/STI risk reduction counseling* • Contraception counseling • PrEP counseling 								
Clinical	
 • Review/update medical history • Review/update concomitant medications and vaginal products • Targeted physical exam* • Pelvic exam* • Collect AEs • Treat RTI/UTI/STIs* • Disclose available test results 								
Laboratory	
 
 Urine	 
 • Urine dipstick and/or culture* • Pregnancy test* 	
 
 Blood	 
 • HIV-1 testing* • AST/ALT* • Creatinine clearance* • CBC with platelets* • Syphilis serology* • Plasma for DPV drug levels (DPV group) • DBS for FTC-TP & TFV-DP drug levels (Truvada group) 	
 
 Breast milk	 
 • Breast milk for DPV drug levels (DPV group) • Breast milk for FTC & TFV drug levels (Truvada group) 	
 
 Pelvic	 
 • NAAT for GC/CT/TV* • Wet prep/KOH wet mount for candidiasis and/or BV* • Vaginal pH* 	
 
	Urine	
 • Urine dipstick and/or culture* • Pregnancy test* 	Blood	
 • HIV-1 testing* • AST/ALT* • Creatinine clearance* • CBC with platelets* • Syphilis serology* • Plasma for DPV drug levels (DPV group) • DBS for FTC-TP & TFV-DP drug levels (Truvada group) 	Breast milk	
 • Breast milk for DPV drug levels (DPV group) • Breast milk for FTC & TFV drug levels (Truvada group) 	Pelvic	
 • NAAT for GC/CT/TV* • Wet prep/KOH wet mount for candidiasis and/or BV* • Vaginal pH*

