7.6 Participants who Discontinue Breastfeeding

Mothers who discontinue breastfeeding (e.g., due to decision to wean) will continue to receive study product and will continue with all regularly scheduled visits for the duration of their originally

scheduled participation in MTN-043. Reasons for discontinuation of breastfeeding will be captured on CRFs.

Infants of mothers who report complete discontinuation of breastfeeding will discontinue drug detection procedures and remain in follow-up for the duration of their originally scheduled participation in MTN-043.

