3. GENERAL DATA ANALYSIS CONSIDERATIONS

3.1 Analysis Set(s)

Following the intent to treat (ITT) approach, participants will be classified by their randomized study arm regardless of the study product received. Participants found to be ineligible post-enrollment will be excluded from all analyses. For the primary safety endpoints (maternal safety, infant safety) participants enrolled and who received at least one dose of study product will be included. All participants with at least one post-enrollment drug concentration result will be included in the primary analysis for drug detection.

For analysis of drug concentrations, a secondary analysis will be conducted including only visits in which a participant has been exposed to the study product and excluding visits of mothers or infants with mothers terminating the study early or on product hold.

For the secondary endpoint of adherence, all mothers will be included. However, reasons for study product non-use from all mothers will be tabulated. A secondary sensitivity analysis will be conducted including only mothers with drug concentration results for at least one visit after Enrollment.

For the secondary endpoint of acceptability, all mothers with non-missing responses for the acceptability and preference questions (#1, #2, #5, #6 and #7) on the Behavioral Assessment – Month 3 Follow Up

eCRF will be included. Mothers with some missing responses to the identified questions will be included in each part of the acceptability analysis as appropriate.

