3.2 Statistical Analysis Issues

In the spirit of the ITT approach, data collected outside of a participant's visit window will be included in the analysis.

Due to the occurrence of a pandemic during the conduct of this study, there may be more than expected missing data. Any missing data will be tabulated as a separate category when reporting data summaries. If a substantial amount of endpoint data is missing (e.g., follow up data missing in at least 10% of participants), then secondary sensitivity analyses of the endpoints will be conducted using methods that relax the missing completely at random assumption to a missing at random assumption. For a univariate binary and quantitative outcome, respectively, a generalized linear model with a binomial or Normal error distribution will be used for estimation and testing. These secondary sensitivity analyses will include imputing the data under the most extreme scenarios of information missingness, such as assuming participants with missing data has an extreme value of the missing variable.

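### The ever-detected proportion in SAP 8.3 has no tested, on-product denominator for each sample type, so some untested or washout-only participants are read as undetectable

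*SAP*

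**What the plan says.** SAP 8.3 sets the summary: "The proportion of participants with detectable drug levels in each study arm for each sample type will be summarized using descriptive statistics". Anyone above the LLOQ is classed as follows: "for any visit after Enrollment will be considered to have a detectable drug level; otherwise, the participant will be considered to have an undetectable". SAP 8 attaches an exact binomial confidence interval to each primary endpoint, and SAP 2.5 takes the detection event to be a participant with detectable drug.

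The denominator comes from SAP 3.1: "All participants with at least one post-enrollment drug concentration result will be included in the primary analysis for drug detection".

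Samples are taken from mothers at Visits 3-8 and from infants at Visits 4-8. Visit 8 "will occur two weeks (i.e., approximately 14 days) after the PUEV" (Protocol 7.4.4), and SAP 8.3 does not leave it out of the rule.

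Some series are short by design. Protocol 7.6 says: "Infants of mothers who report complete discontinuation of breastfeeding will discontinue drug detection procedures". Protocol 7.5.4 stops drug specimens after the visit at which product is held, until use resumes. SAP 3.2 adds that, because of the pandemic, "there may be more than expected missing data".

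**The concern.** The rule and the analysis set do not fit together at three points.

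- **Sample type.** Detection is reported per sample type, but entry needs only one result of any type. A mother with blood results and no milk result is in the set and, for milk, falls into the default class. Infants give blood only, so this gap concerns mothers.
- **Washout.** A participant whose only result is a Visit 8 sample below the LLOQ was never tested on product, yet counts as undetectable.
- **Short series.** One negative sample gives the same classification as a full set of negatives.

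Each lowers the ever-detected proportion relative to what complete on-product sampling would show. Infant exposure is central to this trial's hypotheses, and an understated proportion makes exposure look rarer than it is.

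**Working it through.** **The plan's own figures.** SAP 2.5 applies its precision figures to detection. For 0 events the exact upper bound is 1 − 0.025^(1/n), which is 2.43% for n = 150 and 7.11% for n = 50. At a 5% true rate, P(0 events) = 0.95^n, which is 0.05% and 7.69%. All four match the SAP. They presume that every participant counted was tested. The documents give no figure for the any-visit rule itself.

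**Short series, infants.** There are four on-product visits (4-7; Visit 7 is the product-use-end visit) plus Visit 8. Assumptions, none given in the documents: per-visit detection p, per-visit missingness m, independent visits, no detections at Visit 8. The denominator is infants with at least one of the five results:

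ever-detected = [1 − (1 − (1 − m)p)^4] / [1 − m^5]

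The divisor differs from 1 by less than 0.0001 for m up to 0.15.

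| p | m = 0 | m = 5% | m = 10% | m = 15% |
|---|---|---|---|---|
| 0.10 | 1 − 0.900^4 = 34.4% | 1 − 0.905^4 = 32.9% | 1 − 0.910^4 = 31.4% | 1 − 0.915^4 = 29.9% |
| 0.20 | 1 − 0.80^4 = 59.0% | 1 − 0.81^4 = 57.0% | 1 − 0.82^4 = 54.8% | 1 − 0.83^4 = 52.5% |

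The drops are 1.5 and 2.1 points at 5% missing, 3.0 and 4.3 at 10%, and 4.5 and 6.5 at 15%. The 5% column corresponds roughly to the 95% retention target in Protocol 5.1.2. If all of an infant's samples gave the same result, one sample would be enough and the drop would be zero, so correlation pulls these figures down.

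For scale, 3/4 of the 197 enrolled pairs is about 148 (the actual split is not given). The approximate 95% half-width is 1.96 × √(0.344 × 0.656/148) = 7.7 points at 34.4%, and 7.9 points at 59.0%.

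**Missing sample type, mothers.** Assume 15 of 148 ring-arm mothers (about 10%) have plasma but no milk result. If 127 of the 133 tested are positive, the proportion among those tested is 127/133 = 95.5%. With the 15 counted as undetectable it is 127/148 = 85.8%. If 67 are positive, the figures are 50.4% and 45.3%.

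**Visit 8.** Protocol 2.7.2 gives dapivirine terminal half-lives of 35.2 h (plasma) and 39.0 h (milk). The fraction left at 14 days (336 h) is 2^(−336/35.2) = 0.13% in plasma and 2^(−336/39.0) = 0.26% in milk. At 7 days, the earliest the visit window allows, it is 3.7% and 5.1%. From the median peaks of 327 and 676 pg/mL quoted there, this leaves about 0.4 and 1.7 pg/mL at day 14, and 12 and 34 pg/mL at day 7. No LLOQ is given, and no half-life for FTC-TP or TFV-DP, so the Truvada arm cannot be assessed in this way.

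**The case against.** The plan has real safeguards. Participants with no post-enrollment result are excluded, not called negative. SAP 3.2 tabulates missing data as a separate category and adds sensitivity analyses, including extreme-value imputation, when a substantial amount is missing (10% of participants is its example). SAP 3.1 plans a secondary analysis of drug concentrations on product-exposed visits only, and SAP 8.3 reports concentrations by visit. So a reader who infers that missing samples in general count as negatives goes further than the text. What stands is narrower. A participant with one negative and several missed samples already has a classification under 8.3, so 3.2 may not treat that endpoint as missing. The exposed-visits analysis is secondary and does not address missed samples.

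A reader might also infer that Visit 8 biases detection downward. Under an any-positive rule it cannot, except where it is the only result. Counting it as a fifth visit equally likely to be positive gives 41.0% falling to 35.9% at 15% missing (p = 0.10), and 67.2% falling to 60.6% (p = 0.20). Those drops of 5.1 and 6.6 points assume washout samples behave like on-product ones, which is hard to defend.

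For weaned infants, sampling stops when exposure through milk stops, so the later visits are not plainly lost opportunities. That is a fair point, and a reason to show results by number of samples tested instead of imputing.

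Finally, ever-detected suits the hypothesis that drug will be found in some infants, and no mother-infant comparison is planned. Both points are accepted: the documents do not support replacing the measure, or treating the different numbers of maternal and infant samples as an error.

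**Conclusion.** The gap is real but limited. Taken literally, SAP 8.3 with SAP 3.1 misclassifies two groups as undetectable: participants with no result for a sample type, and those with only a below-LLOQ Visit 8 result. It also treats partial and complete all-negative series alike. How many participants are affected cannot be known from the documents.

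For partial infant series the downward effect is about 1.5-2 points at 5% missing and 4.5-6.5 points at 15%. This rests on four on-product visits, independence, no Visit 8 detections and 10-20% detection per visit, and it shrinks with within-infant correlation. At 5% missing it is small against a half-width of about 8 points; at 15% it is not. The missing-sample-type effect in mothers is roughly the untested fraction multiplied by the true proportion. Visit 8 should seldom change a mother's dapivirine status. The effect in infants and in the Truvada arm cannot be quantified.

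**What to change.** Amend SAP 3.1 and 8.3 as follows.

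- Keep the ever-detected proportion, defined separately for each sample type among participants with at least one on-product result of that type (mothers Visits 3-7, infants Visits 4-7).
- Report participants without such a result as missing, so that 8.3 agrees with 3.2.
- Tabulate the proportion by number of samples tested.
- Beside it, give the proportion above the LLOQ at each on-product visit among those tested, with exact 95% CIs.
- Report Visit 8 separately as washout.

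The cost is SAP wording, a few extra table rows and slightly smaller denominators. By-visit concentration tables are already planned, and no new data are needed.

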A growing body of evidence supports the use of Truvada in breastfeeding women.^{45,46} Mugwanya and colleagues conducted a prospective short-term, open-label study of daily oral FTC/TDF PrEP among 50 HIV-uninfected breastfeeding African mother–infant pairs between 1–24 weeks postpartum. The primary aim was to quantify steady-state concentrations of TFV and FTC in infant plasma ingested via breastfeeding. PrEP was given to women through daily directly observed therapy (DOT) for ten consecutive days and discontinued thereafter. Overall, median (IQR) time-averaged peak concentrations in breast milk were 3.2 ng/mL (2.3 to 4.7) for TFV and 212.5 ng/mL (140.0 to 405.0) for FTC. Similarly, median (IQR) time-averaged trough concentrations in breast milk were 3.3 ng/mL (2.3 to 4.4) for TFV and 183.0 ng/mL (113.0 to 250.0) for FTC, reflecting trough-to-peak breast milk concentration ratios of 1.0 for TFV and 0.8 for FTC, respectively. In infant plasma, TFV was unquantifiable in 46/49 samples (94%), and FTC was detectable in 47/49

(96%) (median [IQR] concentration: 13.2 ng/mL [9.3 to 16.7]). Estimated equivalent doses an infant would ingest daily from breastfeeding were 0.47 µg/kg (IQR 0.35 to 0.71) for TFV and 31.9 µg/kg (IQR 21.0 to 60.8) for FTC, equivalent to a <0.01% and 0.5% relative dose when compared to the 6 mg/kg dose that is proposed for therapeutic treatment of infant HIV infection and for prevention of infant postnatal HIV infection; a dose that has not shown safety concerns. No serious adverse effects were recorded during study follow-up. These data suggest Truvada could be safely used during breastfeeding with minimal infant drug exposure.⁴⁵ Results from the International Maternal, Pediatric, Adolescent AIDS Clinical Trials Group (IMPAACT) PROMISE study also showed that both maternal antiretroviral therapy (TDF/FTC/Lopinavir/Ritonavir[LPVr]) and prolonged infant antiretroviral prophylaxis (iNVP) were safe and associated with very low breastfeeding HIV-1 transmission and high infant HIV-1-free survival at 24 months.⁴⁷

Studies of Truvada as PrEP During Pregnancy

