The first study of dapivirine exposure during lactation, MTN-029/IPM 039 (25 mg DPV VR used for 14 days by lactating women who had completed weaning their infants), found no significant safety concerns in women and extremely low levels of dapivirine in breast milk and maternal blood. Estimated levels of infant dapivirine exposure were also low. Based on these data, it is reasonable to expect that dapivirine will be detectable in both blood and breast milk of breastfeeding mothers at low levels. However, given the low levels of dapivirine anticipated in breast milk, and the poor oral bioavailability of dapivirine, it is not anticipated that infants will have detectable levels of dapivirine in their blood. It is not anticipated that participation in MTN-043 will pose significant safety concerns for either women or their breastfeeding infants.

Truvada, as an approved drug in many settings, already has guidance for prescribers that includes available data on the potential effect of drug exposure on breastfeeding infants. Additionally, drug exposure in breastfeeding infants is low. Based on data from Mugwanya et al⁴⁵, FTC and TDF are detected in breast milk at very low concentrations (0.3–2% of the levels required for infant treatment). In recent guidance, WHO stated that existing safety data support the use of PrEP in pregnant and breastfeeding women who are at continuing substantial risk of HIV infection. However, WHO also acknowledged that more data are needed on TDF and FTC/TDF safety during breastfeeding. Not all countries that have approved FTC/TDF for PrEP have approved its use for breastfeeding women, presumably due to the desire for additional safety data.⁶⁶

In summary, the emerging evidence on increased risk of HIV infection during the postnatal period, the ethical imperative to include mothers and breastfeeding infants in drug safety studies, and the limited but favorable safety profiles for DPV and Truvada in these populations supports this evaluation of DPV and Truvada by breastfeeding mother-infant pairs in Sub-Saharan African countries with high incidence of sexually transmitted HIV infection.

Safeguards to Mitigate Risk

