12. CHANGE HISTORY

Identify major changes. Only changes after version 1.0 approval need to be recorded.

Version		Affected Section(s)	Activity Description
Number	Effective Date		
2.0	Nov. 4, 2022	Title page, ToC, Sections 1, 2.3, 3.1, 3.2, 5, 6.1, 6.2, 8, 8.3, 9.1, 9.2, 10, 10.1, 10.4, 10.7.	
 - Added an effective date on title page per SCHARP guidelines - Updated Table of Contents - Clarified that the intent to treat (ITT) approach is not a modified ITT and provided more detail of participants included in the analysis. Changes made in the acronyms section 1.0 and sections 3.1, 3.2, and 8. - Removed the ambiguous text about less informative imputation in section 3.2. - Changed to summaries with the number of non-missing values rather than the number of missing values as described in section 5. - In section 6.1, a reference to section 3.1 was added. - Clarified that infant consent was made by the infant's mother in section 6.3. - To section 8.3, added arithmetic mean, standard deviation, and number of detectable drug levels to drug concentration summaries. The natural log transformations will not be used but figures will be presented using the log scale. Box plots with medians will be used to present drug concentrations over study timepoints. - Provided specific details for secondary adherence endpoint analysis description in section 9.1. Adherence defined as "no use" (rather than "consistent study product use") with identified cut-points for the study products. Dapivirine (DPV) release rate defined for the DPV ring arm. Further details provided for the comparison (GEE) models. Added an explanation of the differences from the protocol. - Clarified that Questions #1 and #2 are study product arm specific. - Removed first sentence of section 10 with clarification provided in section 3.1. - In sections 10.1 and 10.4, clarified that number and percentages of participants with AEs or abnormal pelvic exam findings will be included in addition to the number and percentages of AEs or pelvic exam findings in the summaries. - In section 10.7, text for "Genital Infections" and "other vaginal findings" was added for clarification. - Made grammatical and typographical error corrections (2.3, 3.1, 6.2, 8.3)

From: [[name]](#)
To: [[name]](#)
Subject: RE: MTN043 SAP version 2.0 approval
Date: Thursday, October 20, 2022 4:06:59 PM

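### SAP 8.3 names a geometric CV but gives the arithmetic CV formula; separately, it has no rule for cells in which most values fall below the LLOQ

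*SAP*

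**What the plan says.** SAP 8.3 (Drug Detection) lists the summaries for drug concentrations: "geometric mean, geometric coefficient of variation (CV), arithmetic mean, standard deviation (SD), median", then IQR and range, plus the number and percentage of participants with detectable and undetectable levels. The geometric CV is the only CV in the list. The formula follows in the same paragraph. It begins "The CV will be calculated as" and continues with 100 times the standard deviation divided by the mean of the concentration values.

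For results below the assay limit the same section says "we will use a value equivalent to half the LLOQ". It sets no fraction below the LLOQ at which a summary is withheld or flagged, offers no alternative estimator, and states no LLOQ. Concentrations are tabulated for each visit, by study site.

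The SAP change history for version 2.0 records that arithmetic mean and SD were added to these summaries and that "The natural log transformations will not be used but figures will be presented using the log scale".

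The documents point in different directions on how often infant samples will be quantifiable:

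- Protocol 2.11 says of dapivirine that "it is not anticipated that infants will have detectable levels of dapivirine in their blood".
- Protocol 10.3 hypothesises that dapivirine will be detectable in some infants.
- Protocol 2.8.2 cites a 10-day oral PrEP study in which infant plasma tenofovir was unquantifiable in 46 of 49 samples and emtricitabine was detectable in 47 of 49.

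**The concern.** A geometric CV is computed from the SD on the log scale. SD over mean of the untransformed values is a different statistic. A programmer following SAP 8.3 must either print an arithmetic CV under a geometric label or depart from the written formula. Two analysts could produce different tables from the same data and both claim to follow the plan.

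The second issue arises only in cells with mostly unquantifiable values. Replacing all of them by one constant makes the geometric mean and CV depend mainly on that constant. Protocol 2.11 says the drug detection endpoints were chosen partly for their importance to future labelling. A reader could take such an infant geometric mean for a measured exposure.

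**Working it through.** The plan states no CV, geometric mean or LLOQ, so there is no figure of its own to reproduce.

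**Inputs**

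Log-scale SD, assuming lognormality: s = ln(Q3/Q1) / (2 × 0.6745).

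- Maternal plasma dapivirine, IQR 274.5–378 pg/mL (Protocol 2.7.2): s = 0.237.
- Milk dapivirine, IQR 443–924.5 pg/mL (Protocol 2.7.2): s = 0.545.
- Milk emtricitabine, peak, IQR 140–405 ng/mL (Protocol 2.8.2): s = 0.787.

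Cell sizes: 197 enrolled pairs at 3:1 gives about 148 and 49 (197 × 3/4 = 147.75; 197/4 = 49.25). An average of 49/4 ≈ 12 Truvada pairs per site follows from the four sites.

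**Step 1: the two formulas**

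- Stated: 100 × SD / mean.
- Geometric: 100 × sqrt(exp(s²) − 1).

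For lognormal data both have the same population value: 24.1%, 58.9% and 92.7% for the three spreads. They differ in finite samples. Simulated medians without censoring, subject to small simulation error:

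| Quantity | n | Stated formula | Geometric formula |
|---|---|---|---|
| Plasma dapivirine | 49 | 23.7% | 23.8% |
| Milk dapivirine | 148 | 57.7% | 58.7% |
| Milk emtricitabine | 49 | 84% | 92% |
| Milk emtricitabine | 12 | 75% | 89% |

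The gap widens with skew and with smaller cells.

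**Step 2: half-LLOQ substitution when most values are below the LLOQ**

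Set LLOQ = 1 and let a fraction c fall below it. With z the standard normal quantile of c and φ the normal density:

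- true geometric mean = exp(−s z);
- ln(substituted geometric mean) = c ln(0.5) + s φ(z) − s z (1 − c).

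Take c = 0.94 as an illustration, so z = 1.555 and φ(z) = 0.119:

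| s | True GM | Substituted GM | Ratio | True CV | Stated formula | Geometric formula |
|---|---|---|---|---|---|---|
| 0.237 | 0.69 | 0.52 | 0.76 | 24% | 28% | 19% |
| 0.545 | 0.43 | 0.53 | 1.2 | 59% | 37% | 23% |
| 0.787 | 0.29 | 0.53 | 1.8 | 93% | 49% | 26% |

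The substituted geometric mean hardly moves while the true one more than halves. Under this censoring the stated formula gives the larger CV of the two.

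**Step 3: dependence on the constant**

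Take 46 of 49 values below the LLOQ and assume the other three are at 2 × LLOQ.

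- With LLOQ/2: mean = (46 × 0.5 + 3 × 2)/49 = 0.592, SD = 0.363, so the stated CV is 61%. The geometric formula gives 35%, and the geometric mean is 0.54.
- With LLOQ in place of LLOQ/2: the geometric mean is 2^(3/49) = 1.04 and the stated CV is 23%.

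The geometric mean nearly doubles because the constant doubled. Above 50% below the LLOQ, the median also equals the constant.

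**Step 4: light censoring**

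At 10–25% below the LLOQ, the substituted geometric mean stays within about 9% of the truth for s from 0.545 to 1.5 (values above 0.787 are assumptions).

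**The case against.** The strongest reply is that these are descriptive statistics. No test or decision uses the geometric mean or the CV. The two CVs estimate the same population quantity under lognormality, and at the documents' own spreads they differ by between a tenth of a point and about 14 points (75% against 89%, the smallest cell). Half-LLOQ is a common convention and is specified in advance. The number and percentage detectable, the median, IQR and range are reported alongside, so a reader would see that a cell is mostly unquantifiable. Version 2.0 dropped log transformation and added the arithmetic mean and SD, so the slip may lie in the label and not in the formula.

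Most of this stands, and it limits the size of the point. It does not remove the mismatch: the text still names one statistic and defines another.

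A reader might go further and infer that the primary concentration summaries are computed wrongly, or that the infant results will be artefacts. The documents do not support that:

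- Only the CV has a formula that contradicts its name.
- The 94% unquantifiable figure is plasma tenofovir. This trial measures TFV-DP and FTC-TP in infant dried blood spots, a different analyte and matrix.
- In the same cited study emtricitabine was detectable in 96% of infant samples, and Protocol 10.3 expects dapivirine in some infants.
- Nor is the stated CV always too small. It is the smaller one without censoring and the larger one with heavy censoring.

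**Conclusion.** The CV definition in SAP 8.3 is wrong as written, whichever of label or formula was intended. Its effect is negligible for plasma dapivirine, about one point for milk dapivirine over the whole ring arm, about 8 points for milk emtricitabine at n = 49, and about 14 points at n = 12. These sizes assume lognormal data with the spreads of the cited earlier studies.

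The substitution point is secondary and conditional. If about 94% of a cell is below the LLOQ, the geometric mean sits near 0.53 × LLOQ, which is 0.76 to 1.8 times the truth for log-SDs of 0.237 to 0.787. The direction of error is therefore not fixed, and the CV is likewise driven by the constant. Protocol 2.11 makes this plausible for infant dapivirine, but without an LLOQ in 8.3 the fraction is an assumption. Those spreads come from maternal samples, so applying them to infants is a further assumption.

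It would be too much to conclude that the geometric mean, arithmetic mean, SD, median, IQR or range are mis-defined. The detection proportions, which address the infant detection hypotheses, do not depend on the substituted value.

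**What to change.** 1. In SAP 8.3, define the geometric CV as 100 × sqrt(exp(s²) − 1), with s the SD of ln(concentration). If the arithmetic CV is intended, keep the formula and delete the word geometric. Either choice removes the contradiction.
2. Report the number and percentage below the LLOQ for each visit and matrix, and state each assay's LLOQ.
3. Set in advance a fraction below the LLOQ above which the geometric mean and CV are omitted or flagged. In those cells show the median and other percentiles that fall below the limit as `<LLOQ`, with the maximum. The exact cut-off is a matter of judgement.
4. Optionally, add a censored-lognormal estimate as a sensitivity analysis where enough values are quantified. It would be fragile in small visit-by-site cells and need not replace the main summary.

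The cost is a few SAP lines and minor table programming, with no new data. The downside is that some infant cells will show no geometric mean.
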